...median [IQR]	19.00 [15.00, 25.50]	19.50 [15.00, 27.00]	18.00 [13.50, 24.00]	18.50 [14.00, 26.00]	N/A	N/A	#VALUE!	#VALUE!	#VALUE!
...Missing; n (%)	5,157 (58.1%)	5,041 (56.8%)	8,182 (93.9%)	8,257 (94.7%)	N/A	N/A	13,339 (75.8%)	13,298 (75.6%)	0.00
Lab result number- Creatinine (mg/dl) mean (only 0.1 to 15 included)	3,791	3,936	520	468	N/A	N/A	4,311	4,404	
...mean (sd)	1.20 (0.50)	1.24 (0.51)	1.15 (0.52)	1.18 (0.61)	N/A	N/A	1.19 (0.50)	1.23 (0.52)	-0.08
...median [IQR]	1.08 [0.87, 1.41]	1.14 [0.88, 1.48]	1.00 [0.84, 1.36]	1.01 [0.84, 1.35]	N/A	N/A	1.07 (0.50)	1.13 (0.52)	-0.12
...Missing; n (%)	5,089 (57.3%)	4,944 (55.7%)	8,196 (94.0%)	8,248 (94.6%)	N/A	N/A	13,285 (75.5%)	13,192 (75.0%)	0.01
Lab result number- HDL level (mg/dl) mean (only <5000 included)	2,999	3,087	501	396	N/A	N/A	3,500	3,483	
...mean (sd)	45.64 (13.89)	46.51 (14.12)	43.93 (15.31)	51.64 (174.45)	N/A	N/A	45.40 (14.10)	47.09 (60.26)	-0.04
...median [IQR]	44.00 [36.00, 53.00]	44.50 [37.00, 54.00]	42.50 [35.00, 52.00]	41.00 [34.00, 52.00]	N/A	N/A	43.79 (14.10)	44.10 (60.26)	-0.01
...Missing; n (%)	5,881 (66.2%)	5,793 (65.2%)	8,215 (94.3%)	8,320 (95.5%)	N/A	N/A	14,096 (80.1%)	14,113 (80.2%)	0.00
Lab result number- LDL level (mg/dl) mean (only <5000 included)	3,014	3,106	481	376	N/A	N/A	3,495	3,482	
...mean (sd)	85.21 (41.48)	85.59 (40.41)	86.93 (43.78)	85.05 (45.50)	N/A	N/A	85.45 (41.81)	85.53 (40.99)	0.00
...median [IQR]	81.75 [60.00, 108.00]	82.75 [61.00, 109.00]	85.00 [62.00, 109.58]	84.50 [59.00, 111.38]	N/A	N/A	82.20 (41.81)	82.94 (40.99)	-0.02
...Missing; n (%)	5,866 (66.1%)	5,774 (65.0%)	8,235 (94.5%)	8,340 (95.7%)	N/A	N/A	14,101 (80.1%)	14,114 (80.2%)	0.00
Lab result number- Total cholesterol (mg/dl) mean (only <5000 included)	3,048	3,148	504	402	N/A	N/A	3,552	3,550	
...mean (sd)	172.69 (47.81)	173.80 (47.86)	173.39 (53.59)	173.95 (57.11)	N/A	N/A	172.79 (48.68)	173.82 (49.00)	-0.02
...median [IQR]	166.00 [141.00, 199.00]	166.00 [142.00, 197.50]	168.00 [143.00, 202.88]	170.00 [141.00, 205.00]	N/A	N/A	166.28 (48.68)	166.45 (49.00)	0.00
...Missing; n (%)	5,832 (65.7%)	5,732 (64.5%)	8,212 (94.2%)	8,314 (95.4%)	N/A	N/A	14,044 (79.8%)	14,046 (79.8%)	0.00
Lab result number- Triglyceride level (mg/dl) mean (only <5000 included)	3,015	3,135	499	397	N/A	N/A	3,514	3,532	
...mean (sd)	193.31 (156.70)	189.61 (172.97)	195.78 (174.50)	212.71 (232.81)	N/A	N/A	193.66 (159.37)	192.21 (180.70)	0.01
...median [IQR]	156.00 [112.00, 225.00]	152.00 [107.00, 222.00]	151.00 [105.00, 224.00]	159.00 [107.67, 235.00]	N/A	N/A	155.29 (159.37)	152.79 (180.70)	0.01
...Missing; n (%)	5,865 (66.0%)	5,745 (64.7%)	8,217 (94.3%)	8,319 (95.4%)	N/A	N/A	14,082 (80.0%)	14,064 (79.9%)	0.00

Table 1

Lab result number- Hemoglobin mean (only >0 included)	2,720	2,902	370	352	N/A	N/A	3,090	3,254	
...mean (sd)	13.16 (1.75)	13.17 (1.73)	377.00 (7,000.31)	444.91 (8,100.93)	N/A	N/A	56.73 (2420.26)	59.87 (2661.83)	0.00
...median [IQR]	13.20 [11.90, 14.40]	13.20 [11.95, 14.40]	13.30 [12.00, 14.70]	13.30 [12.00, 14.54]	N/A	N/A	#VALUE!	#VALUE!	#VALUE!
...Missing; n (%)	6,160 (69.4%)	5,978 (67.3%)	8,346 (95.8%)	8,364 (96.0%)	N/A	N/A	14,506 (82.4%)	14,342 (81.5%)	0.02
Lab result number- Serum sodium mean (only >90 and <190 included)	3,702	3,832	514	457	N/A	N/A	4,216	4,289	
...mean (sd)	139.51 (2.85)	139.59 (2.84)	139.02 (3.31)	139.09 (2.65)	N/A	N/A	139.45 (2.91)	139.54 (2.82)	-0.03
...median [IQR]	140.00 [138.00, 141.33]	140.00 [138.00, 141.50]	139.00 [137.50, 141.00]	139.33 [137.00, 141.00]	N/A	N/A	139.88 (2.91)	139.93 (2.82)	-0.02
...Missing; n (%)	5,178 (58.3%)	5,048 (56.8%)	8,202 (94.1%)	8,259 (94.8%)	N/A	N/A	13,380 (76.0%)	13,307 (75.6%)	0.01
Lab result number- Albumin mean (only >0 and <=10 included)	3,422	3,605	447	397	N/A	N/A	3,869	4,002	
...mean (sd)	4.20 (0.35)	4.21 (0.36)	4.04 (0.76)	4.09 (0.71)	N/A	N/A	4.18 (0.42)	4.20 (0.41)	-0.05
...median [IQR]	4.20 [4.00, 4.40]	4.20 [4.00, 4.45]	4.15 [4.00, 4.40]	4.20 [4.00, 4.40]	N/A	N/A	4.19 (0.42)	4.20 (0.41)	-0.02
...Missing; n (%)	5,458 (61.5%)	5,275 (59.4%)	8,269 (94.9%)	8,319 (95.4%)	N/A	N/A	13,727 (78.0%)	13,594 (77.3%)	0.02
Lab result number- Glucose (fasting or random) mean (only 10-1000 included)	3,684	3,829	509	456	N/A	N/A	4,193	4,285	
...mean (sd)	171.75 (75.07)	164.58 (71.69)	171.74 (71.84)	166.42 (76.33)	N/A	N/A	171.75 (74.69)	164.78 (72.21)	0.09
...median [IQR]	153.00 [122.28, 201.33]	146.00 [118.50, 187.00]	152.50 [124.25, 198.50]	145.00 [121.12, 188.00]	N/A	N/A	152.94 (74.69)	145.89 (72.21)	0.10
...Missing; n (%)	5,196 (58.5%)	5,051 (56.9%)	8,207 (94.2%)	8,260 (94.8%)	N/A	N/A	13,403 (76.2%)	13,311 (75.6%)	0.01
Lab result number- Potassium mean (only 1-7 included)	3,791	3,927	523	449	N/A	N/A	4,314	4,376	
...mean (sd)	4.49 (0.46)	4.49 (0.46)	4.34 (0.47)	4.37 (0.50)	N/A	N/A	4.47 (0.46)	4.48 (0.46)	-0.02
...median [IQR]	4.50 [4.20, 4.80]	4.50 [4.20, 4.80]	4.30 [4.00, 4.70]	4.40 [4.07, 4.70]	N/A	N/A	4.48 (0.46)	4.49 (0.46)	-0.02
...Missing; n (%)	5,089 (57.3%)	4,953 (55.8%)	8,193 (94.0%)	8,267 (94.8%)	N/A	N/A	13,282 (75.5%)	13,220 (75.1%)	0.01
Comorbidity Scores									
CCI (180 days)- ICD9 and ICD10									
...mean (sd)	3.36 (2.08)	3.35 (2.10)	2.46 (1.88)	2.45 (1.86)	3.77 (2.14)	3.77 (2.11)	3.47 (2.09)	3.47 (2.07)	0.00
...median [IQR]	3.00 [2.00, 5.00]	3.00 [2.00, 5.00]	2.00 [1.00, 4.00]	2.00 [1.00, 4.00]	4.00 [2.00, 5.00]	4.00 [2.00, 5.00]	3.48 (2.09)	3.48 (2.07)	0.00
Frailty Score: Qualitative Version 365 days as Categories, v1									
...0; n (%)	4,324 (48.7%)	4,263 (48.0%)	2,619 (30.0%)	2,596 (29.8%)	9,977 (29.9%)	9,686 (29.1%)	16,920 (33.2%)	16,545 (32.5%)	0.01
...1 to 2; n (%)	2,752 (31.0%)	2,873 (32.4%)	3,661 (42.0%)	3,717 (42.6%)	10,036 (30.1%)	10,218 (30.7%)	16,449 (32.3%)	16,808 (33.0%)	-0.01
...3 or more; n (%)	1,804 (20.3%)	1,744 (19.6%)	2,436 (27.9%)	2,403 (27.6%)	13,306 (39.9%)	13,415 (40.3%)	17,546 (34.5%)	17,562 (34.5%)	0.00
Frailty Score: Empirical Version 365 days as Categories,									
...<0.12908; n (%)	1,119 (12.6%)	1,228 (13.8%)	1,240 (14.2%)	1,338 (15.4%)	1,500 (4.5%)	1,563 (4.7%)	3,859 (7.6%)	4,129 (8.1%)	-0.02
...0.12908 - 0.1631167; n (%)	2,577 (29.0%)	2,521 (28.4%)	2,640 (30.3%)	2,578 (29.6%)	5,589 (16.8%)	5,398 (16.2%)	10,806 (21.2%)	10,497 (20.6%)	0.01
...>=0.1631167; n (%)	5,184 (58.4%)	5,131 (57.8%)	4,836 (55.5%)	4,800 (55.1%)	26,230 (78.7%)	26,358 (79.1%)	36,250 (71.2%)	36,289 (71.3%)	0.00
Non-Frailty; n (%)	4,985 (56.1%)	5,157 (58.1%)	4,680 (53.7%)	4,703 (54.0%)	1,469 (4.4%)	1,398 (4.2%)	11,134 (21.9%)	11,258 (22.1%)	0.00
Frailty Score (mean): Qualitative Version 365 days, v1									
...mean (sd)	1.34 (1.92)	1.33 (1.90)	1.80 (1.89)	1.79 (1.89)	2.36 (2.43)	2.36 (2.39)	2.09 (2.26)	2.08 (2.23)	0.00
...median [IQR]	1.00 [0.00, 2.00]	1.00 [0.00, 2.00]	1.00 [0.00, 3.00]	1.00 [0.00, 3.00]	2.00 [0.00, 4.00]	2.00 [0.00, 4.00]	1.65 (2.26)	1.65 (2.23)	0.00
Frailty Score (mean): Empirical Version 365 days,									
...mean (sd)	0.19 (0.06)	0.18 (0.06)	0.17 (0.05)	0.17 (0.05)	0.21 (0.07)	0.21 (0.07)	0.20 (0.07)	0.20 (0.07)	0.00
...median [IQR]	0.17 [0.14, 0.21]	0.17 [0.14, 0.21]	0.16 [0.14, 0.20]	0.16 [0.14, 0.19]	0.20 [0.17, 0.25]	0.20 [0.17, 0.25]	0.19 (0.07)	0.19 (0.07)	0.00
Healthcare Utilization									
Any hospitalization; n (%)	951 (10.7%)	916 (10.3%)	906 (10.4%)	897 (10.3%)	4,351 (13.1%)	4,278 (12.8%)	6,208 (12.2%)	6,091 (12.0%)	0.01
Any hospitalization within prior 30 days; n (%)	309 (3.5%)	317 (3.6%)	272 (3.1%)	263 (3.0%)	1,445 (4.3%)	1,387 (4.2%)	2,026 (4.0%)	1,967 (3.9%)	0.01
Any hospitalization during prior 31-180 days; n (%)	693 (7.8%)	651 (7.3%)	677 (7.8%)	677 (7.8%)	3,166 (9.5%)	3,174 (9.5%)	4,536 (8.9%)	4,502 (8.8%)	0.00
Endocrinologist Visit; n (%)	1,343 (15.1%)	1,478 (16.6%)	1,393 (16.0%)	1,466 (16.8%)	5,278 (15.8%)	5,440 (16.3%)	8,014 (15.7%)	8,384 (16.5%)	-0.02
Endocrinologist Visit (30 days prior); n (%)	991 (11.2%)	1,058 (11.9%)	1,024 (11.7%)	1,071 (12.3%)	3,820 (11.5%)	3,835 (11.5%)	5,835 (11.5%)	5,964 (11.7%)	-0.01
Endocrinologist Visit (31 to 180 days prior); n (%)	887 (10.0%)	950 (10.7%)	917 (10.5%)	947 (10.9%)	3,673 (11.0%)	3,706 (11.1%)	5,477 (10.8%)	5,603 (11.0%)	-0.01
Internal medicine/family medicine visits; n (%)	7,278 (82.0%)	7,050 (79.4%)	7,636 (87.6%)	7,551 (86.6%)	28,049 (84.2%)	27,792 (83.4%)	42,963 (84.4%)	42,393 (83.3%)	0.03
Internal medicine/family medicine visits (30 days prior); n (%)	5,304 (59.7%)	5,228 (58.9%)	5,717 (65.6%)	5,661 (64.9%)	20,249 (60.8%)	20,237 (60.7%)	31,270 (61.4%)	31,126 (61.1%)	0.01
Internal medicine/family medicine visits (31 to 180 days prior); n (%)	6,220 (70.0%)	6,222 (70.1%)	6,651 (76.3%)	6,585 (75.6%)	24,952 (74.9%)	25,013 (75.1%)	37,823 (74.3%)	37,820 (74.3%)	0.00
Cardiologist visit; n (%)	3,365 (37.9%)	3,383 (38.1%)	2,819 (32.3%)	2,869 (32.9%)	14,336 (43.0%)	14,230 (42.7%)	20,520 (40.3%)	20,482 (40.2%)	0.00
Number of Cardiologist visits (30 days prior); n (%)	1,244 (14.0%)	1,238 (13.9%)	963 (11.0%)	974 (11.2%)	4,841 (14.5%)	4,850 (14.6%)	7,048 (13.8%)	7,062 (13.9%)	0.00
Number of Cardiologist visits (31 to 180 days prior); n (%)	2,851 (32.1%)	2,880 (32.4%)	2,408 (27.6%)	2,477 (28.4%)	12,553 (37.7%)	12,531 (37.6%)	17,812 (35.0%)	17,888 (35.1%)	0.00
Electrocardiogram ; n (%)	3,280 (36.9%)	3,359 (37.8%)	3,176 (36.4%)	3,230 (37.1%)	13,574 (40.7%)	13,706 (41.1%)	20,030 (39.3%)	20,295 (39.9%)	-0.01
Use of glucose test strips; n (%)	423 (4.8%)	427 (4.8%)	410 (4.7%)	399 (4.6%)	1,375 (4.1%)	1,338 (4.0%)	2,208 (4.3%)	2,164 (4.3%)	0.00
Dialysis; n (%)	0 (0.0%)	0 (0.0%)	0 (0.0%)	0 (0.0%)	0 (0.0%)	0 (0.0%)	0 (0.0%)	0 (0.0%)	#DIV/0!
Naive new user ; n (%)	2,349 (26.5%)	2,521 (28.4%)	2,348 (26.9%)	2,409 (27.6%)	7,673 (23.0%)	8,355 (25.1%)	12,370 (24.3%)	13,285 (26.1%)	-0.04

Table 1

N antidiabetic drugs at index date									
...mean (sd)	1.76 (0.70)	1.75 (0.68)	1.77 (0.72)	1.77 (0.70)	1.73 (0.70)	1.73 (0.67)	1.74 (0.70)	1.74 (0.68)	0.00
...median [IQR]	2.00 [1.00, 2.00]	2.00 [1.00, 2.00]	2.00 [1.00, 2.00]	2.00 [1.00, 2.00]	2.00 [1.00, 2.00]	2.00 [1.00, 2.00]	2.00 (0.70)	2.00 (0.68)	0.00
number of different/distinct medication prescriptions									
...mean (sd)	11.06 (5.30)	11.07 (5.36)	10.74 (5.13)	10.66 (5.07)	11.45 (5.09)	11.45 (5.01)	11.26 (5.13)	11.25 (5.08)	0.00
...median [IQR]	10.00 [7.00, 14.00]	10.00 [7.00, 14.00]	10.00 [7.00, 13.00]	10.00 [7.00, 14.00]	11.00 [8.00, 14.00]	11.00 [8.00, 14.00]	10.65 (5.13)	10.65 (5.08)	0.00
Number of Hospitalizations									
...mean (sd)	0.13 (0.41)	0.13 (0.41)	0.12 (0.38)	0.12 (0.39)	0.17 (0.48)	0.16 (0.48)	0.15 (0.45)	0.15 (0.45)	0.00
...median [IQR]	0.00 [0.00, 0.00]	0.00 [0.00, 0.00]	0.00 [0.00, 0.00]	0.00 [0.00, 0.00]	0.00 [0.00, 0.00]	0.00 [0.00, 0.00]	0.00 [0.00, 0.00]	0.00 [0.00, 0.00]	0.00
Number of hospital days									
...mean (sd)	0.65 (2.51)	0.67 (2.66)	0.63 (2.74)	0.66 (2.86)	1.03 (3.87)	1.02 (3.97)	0.90 (3.49)	0.90 (3.60)	0.00
...median [IQR]	0.00 [0.00, 0.00]	0.00 [0.00, 0.00]	0.00 [0.00, 0.00]	0.00 [0.00, 0.00]	0.00 [0.00, 0.00]	0.00 [0.00, 0.00]	0.00 [0.00, 0.00]	0.00 [0.00, 0.00]	0.00
Number of Emergency Department (ED) visits									
...mean (sd)	0.50 (1.18)	0.49 (1.40)	0.19 (1.07)	0.19 (1.26)	0.63 (1.43)	0.63 (1.44)	0.53 (1.33)	0.53 (1.40)	0.00
...median [IQR]	0.00 [0.00, 0.00]	0.00 [0.00, 0.00]	0.00 [0.00, 0.00]	0.00 [0.00, 0.00]	0.00 [0.00, 0.00]	0.00 [0.00, 0.00]	0.00 [1.33]	0.00 [1.40)	0.00
Number of Office visits									
...mean (sd)	5.54 (4.50)	5.53 (4.36)	5.93 (5.53)	5.86 (4.31)	6.33 (4.88)	6.36 (4.75)	6.12 (4.93)	6.13 (4.61)	0.00
...median [IQR]	4.00 [2.00, 7.00]	5.00 [3.00, 7.00]	5.00 [3.00, 8.00]	5.00 [3.00, 8.00]	5.00 [3.00, 9.00]	5.00 [3.00, 9.00]	4.83 (4.93)	5.00 (4.61)	-0.04
Number of Endocrinologist visits									
...mean (sd)	0.69 (2.65)	0.80 (2.89)	0.72 (2.77)	0.83 (3.11)	0.94 (3.83)	0.94 (3.69)	0.86 (3.48)	0.90 (3.47)	-0.01
...median [IQR]	0.00 [0.00, 0.00]	0.00 [0.00, 0.00]	0.00 [0.00, 0.00]	0.00 [0.00, 0.00]	0.00 [0.00, 0.00]	0.00 [0.00, 0.00]	0.00 [3.48)	0.00 [3.47)	0.00
Number of internal medicine/family medicine visits									
...mean (sd)	10.20 (14.44)	9.35 (14.18)	7.99 (10.52)	7.84 (10.00)	8.97 (12.50)	8.98 (11.60)	9.02 (12.55)	8.85 (11.84)	0.01
...median [IQR]	6.00 [2.00, 13.00]	5.00 [1.00, 12.00]	5.00 [2.00, 10.00]	5.00 [2.00, 10.00]	5.00 [2.00, 12.00]	6.00 [2.00, 12.00]	5.17 (12.55)	5.65 (11.84)	-0.04
Number of Cardiologist visits									
...mean (sd)	1.85 (4.06)	1.95 (4.53)	1.46 (3.59)	1.47 (3.43)	2.25 (5.02)	2.33 (5.16)	2.04 (4.64)	2.12 (4.80)	-0.02
...median [IQR]	0.00 [0.00, 2.00)	0.00 [0.00, 2.00)	0.00 [0.00, 1.00]	0.00 [0.00, 1.00]	0.00 [0.00, 2.00)	0.00 [0.00, 2.00)	0.00 (4.64)	0.00 (4.80)	0.00
Number of electrocardiograms received									
...mean (sd)	0.76 (1.49)	0.76 (1.50)	0.68 (1.29)	0.67 (1.22)	0.86 (1.52)	0.86 (1.50)	0.81 (1.48)	0.81 (1.46)	0.00
...median [IQR]	0.00 [0.00, 1.00]	0.00 [0.00, 1.00]	0.00 [0.00, 1.00]	0.00 [0.00, 1.00]	0.00 [0.00, 1.00]	0.00 [0.00, 1.00]	0.00 (1.48)	0.00 (1.46)	0.00
Number of HbA1c tests ordered									
...mean (sd)	1.31 (0.95)	1.30 (0.94)	0.99 (0.95)	0.98 (0.93)	1.47 (1.03)	1.47 (0.91)	1.36 (1.00)	1.36 (0.92)	0.00
...median [IQR]	1.00 [1.00, 2.00]	1.00 [1.00, 2.00]	1.00 [0.00, 2.00]	1.00 [0.00, 2.00]	1.00 [1.00, 2.00]	1.00 [1.00, 2.00]	1.00 (1.00)	1.00 (0.92)	0.00
Number of glucose tests ordered									
...mean (sd)	0.80 (6.63)	0.93 (7.31)	0.49 (2.13)	0.49 (1.26)	0.55 (1.52)	0.57 (1.31)	0.58 (3.16)	0.62 (3.27)	-0.01
...median [IQR]	0.00 [0.00, 0.00)	0.00 [0.00, 1.00]	0.00 [0.00, 0.00]	0.00 [0.00, 1.00]	0.00 [0.00, 1.00)	0.00 [0.00, 1.00]	0.00 (3.16)	0.00 (3.27)	0.00
Number of lipid tests ordered									
...mean (sd)	1.04 (1.03)	1.03 (1.00)	0.85 (1.36)	0.86 (1.33)	1.08 (0.95)	1.08 (0.89)	1.03 (1.05)	1.03 (1.00)	0.00
...median [IQR]	1.00 [0.00, 2.00]	1.00 [0.00, 2.00]	1.00 [0.00, 1.00]	1.00 [0.00, 1.00]	1.00 [0.00, 2.00]	1.00 [0.00, 2.00]	1.00 (1.05)	1.00 (1.00)	0.00
Number of creatinine tests ordered									
...mean (sd)	0.06 (0.33)	0.07 (0.47)	0.07 (0.44)	0.07 (0.58)	0.10 (0.47)	0.09 (0.40)	0.09 (0.44)	0.08 (0.45)	0.02
...median [IQR]	0.00 [0.00, 0.00]	0.00 [0.00, 0.00]	0.00 [0.00, 0.00]	0.00 [0.00, 0.00]	0.00 [0.00, 0.00]	0.00 [0.00, 0.00]	0.00 (0.44)	0.00 (0.45)	0.00
Number of BUN tests ordered									
...mean (sd)	0.04 (0.27)	0.04 (0.38)	0.04 (0.38)	0.05 (0.58)	0.06 (0.39)	0.06 (0.32)	0.05 (0.37)	0.05 (0.39)	0.00
...median [IQR]	0.00 [0.00, 0.00]	0.00 [0.00, 0.00]	0.00 [0.00, 0.00]	0.00 [0.00, 0.00]	0.00 [0.00, 0.00]	0.00 [0.00, 0.00]	0.00 (0.37)	0.00 (0.39)	0.00
Number of tests for microalbuminuria									
...mean (sd)	0.89 (1.29)	0.87 (1.32)	0.58 (1.12)	0.57 (1.04)	0.56 (0.85)	0.56 (0.84)	0.62 (0.99)	0.62 (0.98)	0.00
...median [IQR]	0.00 [0.00, 2.00)	0.00 [0.00, 2.00)	0.00 [0.00, 1.00]	0.00 [0.00, 1.00]	0.00 [0.00, 1.00]	0.00 [0.00, 1.00]	0.00 (0.99)	0.00 (0.98)	0.00
Total N distinct ICD9/ICD10 diagnoses at the 3rd digit level									
...mean (sd)	7.43 (8.69)	7.35 (8.77)	2.83 (5.33)	2.85 (5.39)	7.78 (9.41)	7.69 (9.43)	6.87 (8.72)	6.80 (8.75)	0.01
...median [IQR]	5.00 [0.00, 11.00]	5.00 [0.00, 11.00]	0.00 [0.00, 4.00]	0.00 [0.00, 4.00]	5.00 [0.00, 12.00]	5.00 [0.00, 12.00]	4.14 (8.72)	4.14 (8.75)	0.00
Use of thiazide; n (%)	1,042 (11.7%)	1,075 (12.1%)	1,002 (11.5%)	1,005 (11.5%)	4,626 (13.9%)	4,591 (13.8%)	6,670 (13.1%)	6,671 (13.1%)	0.00
Use of beta blockers; n (%)	4,537 (51.1%)	4,527 (51.0%)	4,436 (50.9%)	4,413 (50.6%)	19,108 (57.3%)	19,031 (57.1%)	28,081 (55.2%)	27,971 (54.9%)	0.01
Use of calcium channel blockers; n (%)	2,943 (33.1%)	3,037 (34.2%)	2,769 (31.8%)	2,780 (31.9%)	13,117 (39.4%)	12,995 (39.0%)	18,829 (37.0%)	18,812 (36.9%)	0.00

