After review of initial feasibility and power analyses, complete creation of the remaining covariates (see Table 1 below for list of covariates). Again, using the dummy outcome of a 90-day gap in database enrollment, complete a 1:1 PS-matched analysis. The PS should include the complete list of covariates (excluding laboratory values, which are missing in some patients).

- Provide plot of PS distributions stratified by treatment group.

Note- Please refer to **Appendix B**.

- Report covariate balance after matching.

Note- For Table 1, please refer to **Appendix B**.

- Report reasons for censoring by treatment group.

	Overall	Referent	Exposure
Dummy Outcome	0 (0.00%)	0 (0.00%)	0 (0.00%)
Death	1,704 (1.67%)	929 (1.82%)	775 (1.52%)
Start of an additional exposure	4,752 (4.67%)	746 (1.47%)	4,006 (7.87%)
End of index exposure	58,792 (57.74%)	29,602 (58.14%)	29,190 (57.33%)
Specified date reached	18,168 (17.84%)	9,825 (19.30%)	8,343 (16.39%)
End of patient enrollment	9,190 (9.02%)	4,583 (9.00%)	4,607 (9.05%)
Switch to other SUs (for censoring) + nursing home admission	9,224 (9.06%)	5,230 (10.27%)	3,994 (7.84%)

- Report follow-up time by treatment group.

Patient Group	Median Follow-Up Time (Days) [IQR]		
	Optum	MarketScan	Medicare
Overall Patient Population	118 [58-286]	128 [63-304]	137 [65-323]
Referent	122 [65-304]	148 [86-344]	148 [86-344]
Exposure	118 [58-269]	127 [58-303]	127 [58-303]

- Report overall risk of the primary outcome.

	Optum	Marketscan	Medicare
Risk per 1,000 patients	16.55	18.7	42.47

10. Final Power Assessment

Date conducted: 12/01/2019

- Re-calculate power in the appropriate excel table, using the revised number of matched patients from the PS-match in Section 9. All other parameters in the table should be the same as in Section 8. If the study is to be implemented in more than one database, copy and paste excel sheet to report power for each database separately and for the pooled analysis that uses data from all databases together. Power calculations are based on the formulas from Chow et al. (2008).

- Pooled

Non-inferiority Analysis	
Number of patients matched	
Reference	50,915
Exposed	50,915
Risk per 1,000 patients	25.91
Assumed HR from RCT	1
Alpha (2-sided)	0.05
Non-inferiority margin	1.3
Number of events expected	2638.4153
Power	0.999999116

- Optum

Non-inferiority Analysis	
Number of patients matched	
Reference	8,880
Exposed	8,880
Risk per 1,000 patients	16.55
Assumed HR from RCT	1
Alpha (2-sided)	0.05

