Non-inferiority margin	1.3
Number of events expected	293.928
Power	0.613734405

- Marketscan

Non-inferiority Analysis	
Number of patients matched	
Reference	8,716
Exposed	8,716
Risk per 1,000 patients	18.7
Assumed HR from RCT	1
Alpha (2-sided)	0.05
Non-inferiority margin	1.3
Number of events expected	325.9784
Power	0.658551313

- Medicare

Non-inferiority Analysis	
Number of patients matched	
Reference	33,319
Exposed	33,319
Risk per 1,000 patients	42.47
Assumed HR from RCT	1
Alpha (2-sided)	0.05
Non-inferiority margin	1.3
Number of events expected	2830.11586
Power	0.99999974

- Stop analyses until balance and final power assessment are reviewed by primary investigators, FDA, and assigned members of advisory board. Reviewers evaluate the results of the analyses described above in Sections 9 and 10, including numbers of patients, balance in patient characteristics, follow-up time, and reasons for censoring by treatment group, as well as overall rates of outcomes and study power.

Reviewed by PI:	[name]	Date reviewed:	12/9/19
Reviewed by FDA:	[name]	Date reviewed:	12/20/19
Reasons for stopping analysis (if required):			

11. Study Confidence and Concerns

Deadline for voting on study confidence and listing concerns: 12/20/19

- If final feasibility and power analyses are reviewed and approved, proceed to the remaining protocol steps.
- All study team and advisory board members that review this protocol should at this stage provide their level of confidence for the success of the RWD study in the [Google Form](#). This form also provides space for reviewers to list any concerns that they feel may

contribute to a failure to replicate the findings of the RCT, including differences in study populations, poor measurement of study variables, or residual confounding. All responses will be kept confidential and individual-level results will only be shared with the individual respondent.

12. Register study protocol on clinicalTrials.gov

Date conducted:

- Register the study on [clinicalTrials.gov](https://clinicaltrials.gov) and upload this document.

13. Comparative Analyses

Action report name:

Date conducted:

13.1 For primary analysis:

- In the PS-matched cohort from Section 9, calculate the HR for each outcome for linagliptin versus referent patients using a Cox proportional hazards model.

13.2 For secondary analyses:

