Appendix B

BEFORE PS MATCHING

[figure not shown]

Figure 49: Pre-matching propensity score overlap

[figure not shown]

Figure 49: Pre-matching propensity score overlap

[figure not shown]

Figure 24: Pre-matching propensity score overlap

The c-statistics for the propensity score model, pre-matching was 0.728. The post-matching c-statistic was 0.535.

The c-statistics for the propensity score model, pre-matching was 0.724. The post-matching c-statistic was 0.531.

The c-statistics for the propensity score model, pre-matching was 0.732. The post-matching c-statistic was 0.519.

AFTER PS MATCHING

[figure not shown]

Figure 50: Post-matching propensity score overlap

[figure not shown]

Figure 50: Post-matching propensity score overlap

[figure not shown]

Figure 25: Post-matching propensity score overlap

Table 1

Unmatched								
Variable	Optum		MarketScan		Medicare		POOLED	
	Reference- 2nd Generation SUs	Exposure- Linagliptin						
Number of patients	113,991	8,904	114,025	8,736	366,136	33,401	594,152	51,041
Age								
...mean (sd)	69.66 (10.39)	66.94 (11.64)	65.35 (11.87)	63.75 (11.53)	75.67 (7.35)	75.97 (7.44)	72.54 (9.00)	72.30 (9.09)
...median (IQR)	70.00 [64.00, 77.00]	67.00 [59.00, 76.00]	64.00 [57.00, 74.00]	62.00 [56.00, 71.00]	75.00 [70.00, 81.00]	5.00 [70.00, 81.00]	71.93 (9.00)	71.38 (9.09)
Age categories								
...<18 - 54; n (%)	10,233 (9.0%)	1,320 (14.8%)	19,802 (17.4%)	1,718 (19.7%)	0 (0.0%)	0 (0.0%)	30,035 (5.1%)	3,038 (6.0%)
...55 - 64; n (%)	20,561 (18.0%)	2,441 (27.4%)	40,305 (35.3%)	3,535 (40.5%)	4,429 (1.2%)	340 (1.0%)	65,295 (11.0%)	6,316 (12.4%)
...65 - 74; n (%)	44,396 (38.9%)	2,639 (29.6%)	26,643 (23.4%)	1,785 (20.4%)	177,715 (48.5%)	15,653 (46.9%)	248,754 (41.9%)	20,077 (39.3%)
...>75; n (%)	38,801 (34.0%)	2,504 (28.1%)	27,275 (23.9%)	1,698 (19.4%)	183,992 (50.3%)	17,408 (52.1%)	250,068 (42.1%)	21,610 (42.3%)
Gender								
...Males; n (%)	63,640 (55.8%)	4,680 (52.6%)	68,352 (59.9%)	5,051 (57.8%)	175,512 (47.9%)	14,152 (42.4%)	307,504 (51.8%)	23,883 (46.8%)
...Females; n (%)	50,351 (44.2%)	4,224 (47.4%)	45,673 (40.1%)	3,685 (42.2%)	190,624 (52.1%)	19,249 (57.6%)	286,648 (48.2%)	27,158 (53.2%)
Race								
...White; n (%)	N/A	N/A	N/A	N/A	288,259 (78.7%)	23,448 (70.2%)	288,259 (78.7%)	23,448 (70.2%)
...Black; n (%)	N/A	N/A	N/A	N/A	40,279 (11.0%)	4,263 (12.8%)	40,279 (11.0%)	4,263 (12.8%)
...Asian; n (%)	N/A	N/A	N/A	N/A	11,760 (3.2%)	2,180 (6.5%)	11,760 (3.2%)	2,180 (6.5%)

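### Matched Optum arms still differ in age distribution (65-74: 38.7% sulfonylurea vs 29.7% linagliptin, SMD 0.19) despite equal mean age, and the only printed standardised differences are pooled

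*Combined protocol and SAP*

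**What the plan says.** Section 9 orders a 1:1 propensity-score match and describes the score as follows: "The PS should include the complete list of covariates (excluding laboratory values, which are missing in some patients" (the parenthesis closes there). It asks for covariate balance after matching and points to Table 1 in Appendix B. Table 1 shows age both as mean (SD) and in four categories.

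The matched half of Table 1 gives counts and percentages by arm for each database, but its standardised-difference column refers to the pooled data only. Appendix B also prints three pairs of c-statistics, not labelled by database. The first reads "The c-statistics for the propensity score model, pre-matching was 0.728. The post-matching c-statistic was 0.535"; the other two post-matching values are 0.531 and 0.519.

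Section 10 stops the work until balance and power have been reviewed. No numerical threshold for acceptable balance is given. Section 13.1 then sets out the main comparison: "In the PS-matched cohort from Section 9, calculate the HR for each outcome for linagliptin versus referent patients using a Cox proportional hazards model". It states no further covariate adjustment.

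**The concern.** Age is a basic risk factor for the MACE endpoint. A score that contains age in a flexible form, with 8,880 of 8,904 linagliptin patients in Optum retained, should bring the age categories close together. In Optum the 65-74 row hardly moved.

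The two summaries a reader turns to first, post-matching c-statistics near 0.5 and a pooled standardised difference of 0.04, give no sign of this. What remains after matching passes straight into the Section 13.1 hazard ratio, because that section states no later step that would correct it. At stake are the Optum hazard ratio, to a lesser degree the pooled one, and the basis for judging balance at the Section 10 review.

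**Working it through.** **Inputs** (Appendix B, Table 1). Optum matched, 8,880 per arm, sulfonylurea vs linagliptin: 18-54, 1,227 vs 1,313; 55-64, 1,986 vs 2,434; 65-74, 3,436 vs 2,634; 75 and over, 2,231 vs 2,499. Both columns sum to 8,880, so a single mistyped cell is unlikely. Mean age (SD): 66.96 (10.94) vs 66.96 (11.63).

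**Formula.** SMD = (p0 - p1) / sqrt{[p0(1-p0) + p1(1-p1)] / 2}, with p0 the sulfonylurea and p1 the linagliptin proportion.

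**Reproducing the printed figure.** Pooled 65-74: 21,095/50,915 = 0.4143 and 20,047/50,915 = 0.3937. SMD = 0.0206/0.4906 = 0.042, printed as 0.04. From the unmatched pooled counts (248,754/594,152 and 20,077/51,041) the SMD is 0.052. The pooled figure was therefore already small before matching and could not have shown a problem confined to Optum.

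**Optum, 65-74, after matching.** 0.3869 - 0.2966 = 0.0903; 0.0903/0.4722 = 0.191. Before matching: 44,396/113,991 = 0.3895 and 2,639/8,904 = 0.2964, SMD 0.197.

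| Optum age category | SMD before | SMD after |
|---|---|---|
| 18-54 | -0.181 | -0.028 |
| 55-64 | -0.225 | -0.117 |
| 65-74 | +0.197 | +0.191 |
| 75 and over | +0.128 | -0.068 |
| four categories jointly | 0.327 | 0.196 |
| mean age | 0.247 | 0.00 |

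The joint figure is the multinomial SMD, sqrt(d' S^-1 d), with d the vector of differences in proportions and S the average of the two multinomial covariance matrices. After matching it is 0.032 in MarketScan, 0.013 in Medicare and 0.049 pooled. In MarketScan and Medicare no single category exceeds about 0.03. In matched Optum the chi-square for age category by arm is 169.5 on 3 df, and 36.2% of sulfonylurea against 42.2% of linagliptin patients are under 65.

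**Comparison with the c-statistics.** Order the four matched Optum categories by the linagliptin/sulfonylurea ratio: 65-74 (0.77), 18-54 (1.07), 75 and over (1.12), 55-64 (1.23). Category alone then separates the arms with c = 0.551, which is above all three printed post-matching values. What follows from this is taken up under the objection.

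**Size of the bias.** Assume that the treatments have equal effect and that hazard rises by a factor r per year of age, with r from 1.03 to 1.07. The documents give no such figure. The spurious hazard ratio (linagliptin over sulfonylurea) is then the ratio of the mean hazards of the two age distributions.

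- Category version: sum of p1k × r^(ak) divided by sum of p0k × r^(ak), with an assumed typical age ak for each category. Ages 36, 60, 70, 80 give 0.991 to 0.996. Ages 50, 60, 70, 82 give 0.996 to 1.005. That is about -1% to +1%.
- Normal version with equal means: exp{(ln r)² × (11.63² - 10.94²)/2}, where the difference in variances is 15.57. r = 1.03 gives 1.007 and r = 1.07 gives 1.036. That is about +1% to +4%.

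**Pooled effect.** Section 10 expects 293.9 events in Optum. Against the sum of the three database tables (293.9 + 326.0 + 2,830.1 = 3,450.0) this is 8.5%. Against the printed pooled figure of 2,638.4 it is 11.1%. At most, 0.111 × 4% = 0.45%.

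**For scale.** With 293.9 events the 95% confidence limits lie a factor exp(1.96 × 2/sqrt(293.9)) = 1.26 either side of the Optum hazard ratio. With 2,638.4 events the pooled factor is 1.08.

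**The case against.** **Matching worked for most of age.** This stands. A reader might infer from the 65-74 row that matching did nothing for age in Optum, and the table does not support that. The mean-age difference vanished, three of the four categories improved, the joint SMD fell from 0.33 to 0.20, and the sulfonylurea SD moved from 10.39 to 10.94, towards 11.63. Two categories remain beyond the conventional 0.10, a cut-off that the plan itself does not set.

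**The c-statistics do not prove what the model contained.** A reader might infer that, since age category alone gives 0.551, the score cannot include it. That follows only if the score was refitted in the matched sample. If the pre-matching score was simply evaluated in the matched pairs, its c-statistic can be lower than that of a single covariate. The document does not say which was done, and it does not label the three lines by database. Equal means with unequal categories make a linear-only age term plausible, but this is an inference from the counts.

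**A breach of Section 9 is not established.** Section 6.2 lists age simply as a covariate, and Table 1 shows some variables (age, frailty) in both continuous and categorical form. Continuous age can be read as satisfying the complete-list instruction.

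**The imbalance is not concealed.** The Optum percentages stand in the same row as the pooled 0.04, and Section 9 links a separate Optum report whose content is not in the document. What is missing is a standardised difference for each database.

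**Conclusion.** The matched Optum arms differ in age distribution: SMD 0.19 at 65-74 and -0.12 at 55-64, at equal mean age. No balance statistic printed in the document draws attention to it, and no later adjustment is stated. This rests on the printed counts and needs no assumption.

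The bias figures do rest on assumptions: a log-linear age effect of 3% to 7% per year, and either typical category ages or normality. They give roughly -1% to +4% in the Optum hazard ratio, with the sign depending on the approximation, and under about 0.5% in the pooled one. A reader might infer that the primary result is at risk. It is not: both effects are small beside the confidence limits, and the pooled effect is negligible against the 1.3 margin. The point is minor. It matters mainly for the Optum-specific estimate and for how balance is judged.

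**What to change.** Before any hazard ratio is computed:

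1. State in Section 9 how age enters the propensity score. Add the Table 1 age categories or a spline to the linear term, at least in Optum and preferably in all three databases.
2. Re-match, and update Table 1 and the Section 10 counts.
3. Add a standardised-difference column for each database beside the pooled one, and judge balance per database against a stated threshold.
4. Label the c-statistics by database, and say whether the post-matching values come from a refitted score.

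The cost is a re-run of the match, possibly a few lost pairs (the documents do not allow an estimate), three table columns, and a repeat of the Section 10 balance review. Section 13 shows no completed comparative analysis, so the change can still be made without knowledge of results.
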